Natural Treatments for the Management of Emotional Dysregulation in Youth With Non-verbal Learning Disability (NVLD) and/or Autism Spectrum Disorders (ASD)

NCT03757585

April 23, 2025

Statistical Methods

Participants were included in the analysis based on a modified intent to treat analysis plan with the criterion that participants had to be exposed to the study medications for ?2 weeks. Baseline clinical characteristics were examined using Pearson's chi-squared test for dichotomous measures and truncated Poisson regression models for continuous measures (CBCL-AAA and CBCL-AT: lower level [II] of truncation=150, upper level [ul] of truncation=270; SRS: ll=30, ul=90; BRIEF: ll=30, ul=100; YMRS: ul=60; CDI: ul=40). Primary efficacy measures of mania and depression, as well as secondary measures of autism symptoms and executive functioning, were analyzed using mixed-effects Poisson regression models predict the outcome measure of interest from the study group, study week (continuous), and the study group-by-study week interaction, which is the primary effect of interest. Secondary efficacy measures of mania and depression assessed at endpoint were examined using logistic regression models predicting the outcome of interest from the study group. Adverse events (AEs) were analyzed using a Poisson regression model for AE counts and Fisher's exact tests for AE prevalence. All analyses were two-tailed with an alpha level of 0.05 and conducted using Stata (Version 18.1) (StataCorp, 2023).

We also examined the moderating effect of 1) the CBCL Autistic Traits (AT) profile defined by a combined T-score ?195 on the CBCL Withdrawn/Depressed, Social Problems, and Thought Problems scales, and 2) the CBCL-Bipolar (BP) profile defined by a combined T-score ?210 on the CBCL Aggressive Behavior, Attention Problems, and Anxious/Depressed scales. To examine these moderating effects, we added a 3-way interaction term between study group, study visit, and CBCL profile group to each of the models for the primary and secondary outcomes of interest. The moderating effects of the CBCL-AT and CBCL-BP profiles were examined separately.

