This will be a 6-week, open-label, randomized clinical trial study to compare efficacy and tolerability of the natural treatments omega-3 fatty acids, inositol, and NAC in the treatment of mood dysregulation in children and adolescents with NVLD/ASD. Subjects will include youth ages 5-17 years with a non-verbal learning disability (NVLD) or autism spectrum disorder (ASD) and current symptoms of emotional dysregulation. We will enroll 60 subjects to allow for the randomization of 30 subject into each treatment arm.

The full inclusion and exclusion criteria are included below:

A. Inclusion Criteria:

1. Male or female subjects, 5-17 years of age.
2. A previous established diagnosis of non-verbal learning disability (NVLD) or DSM-V Autism Spectrum Disorder and/ or combined T-scores on the Child Behavior Checklist \geq 195 on the Withdrawn + Social Problems + Thought Problems subscales.

3. Current symptoms of emotional dysregulation as indicated by combined T-scores on the Child Behavior Checklist ≥ 180 on the Anxiety/Depression + Aggression + Attention subscales.
4. Subjects and their caregivers must be English-speaking and have a level of understanding sufficient to communicate intelligently with the investigator and study coordinator, and to cooperate with all tests and examinations required by the protocol.
5. Subjects and their caregivers must be willing and able to comply with all study procedures.
6. Each subject and his/her authorized legal representative must understand the nature of the study. The subject's authorized legal representative must sign an informed consent document and the subject must sign an informed assent document.
7. Subject must be able to swallow pills.
8. Subject must have access to a computer with a camera, speaker, microphone, and internet connection.
9. Subjects must be willing to refrain from treatment changes during the study protocol.

B. Exclusion Criteria:

1. Investigator and his/her immediate family; defined as the investigator's spouse, parent, child, grandparent, or grandchild.
2. Serious or unstable illness including hepatic, renal, gastroenterological, respiratory, cardiovascular (including ischemic heart disease), endocrinologic, neurologic, immunologic, or hematologic disease.
3. History of bleeding diathesis, including those with von Willebrand disease.
4. Uncorrected hypothyroidism or hyperthyroidism.

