Families with children and adolescents with NVLD/ASD and emotional dysregulation can speak with their primary care doctor to obtain a prescription for medication to treat mood disorders or receive a referral to a specialist. Available medications for treating severe mood problems in children include atypical antipsychotic medications and mood stabilizers and in some cases antidepressants. The study doctor can discuss the risks and benefits of other treatments with potential participants and their parent/guardian prior to enrollment.

Describe how risks to subjects are minimized, for example, by using procedures which are consistent with sound research design and which do not unnecessarily expose subjects to risk or by using procedures already being performed on the subject for diagnostic or treatment purposes.

All efforts are made to minimize risks to subjects. The protocol is designed to ensure that safety measurements are completed prior to study drug treatment and that the subject's response to study drug is closely monitored. Previous studies by our research group confirm that these study treatments are safe for use in children at these doses. All procedures used in this study are consistent with sound research design and do not unnecessarily expose subjects to risk. Clear drop criteria will be employed, as described below.

We will be using secure Partners workstations to access Vidyo, a videoconferencing platform, in combination with Skills Based Routing (SBR), a patient management software, to conduct the weekly study visits. Both Vidyo and SBR are secure mediums. Partners Information Systems and MGH Health Information Services have already approved this technology for use.

Describe explicitly the methods for ensuring the safety of subjects. Provide objective criteria for removing a subject from the study, for example, objective criteria for worsening disease/lack of improvement and/or unacceptable adverse events. The inclusion of objective drop criteria is especially important in studies designed with placebo control groups.

Each week, a study clinician will record any adverse events.

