Poor response to treatment, leading to drop from the study, will be measures by a CGI-bipolar score that is 2 points higher (more severe) than baseline for more than 2 consecutive weeks or a P-YMRS score that is 30% higher than baseline for more than 2 consecutive weeks only if the P-YMRS is in a clinically significant range of >15. If a subject should score a 4 or higher on the C-SSRS, he or she will be dropped from the study. The study clinician will assess the level of risk and take appropriate actions, including an immediate referral to emergency services.

In addition, drop from the study will occur at clinician discretion for worsening of clinical course, non-compliance with treatment, or inability to tolerate study treatment.

Subjects who fail to keep study appointments or are non-complaint (less than 70% compliance for 2 weeks or longer) may be dropped from the study. If a subject becomes pregnant or is found to be abusing substances during the study, he or she will be dropped from the study. These study subjects will be given a referral for local treatment.

FORESEEABLE RISKS AND DISCOMFORTS

Provide a brief description of any foreseeable risks and discomforts to subjects. Include those related to drugs/devices/procedures being studied and/or administered/performed solely for research purposes. In addition, include psychosocial risks, and risks related to privacy and confidentiality. When applicable, describe risks to a developing fetus or nursing infant.

Potential side effects are few and will be monitored for throughout the research study. Consent forms will clearly list potential treatment side effects. Since they are natural products, it appears that omega-3 fatty acids, inositol, and NAC have a low potential for unwanted side effects or negative effects on the child's growth and development. It should also be noted that no important toxic effects have been reported in previous use in humans and animals.

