NOTE: Regardless of data and safety monitoring plans by the sponsor or others, the principal investigator is ultimately responsible for protecting the rights, safety, and welfare of subjects under his/her care.

Study monitoring will include periodic inspection of all documents at regular intervals by the Principal Investigator and members of study staff. Such documents will include diagnostic testing, evaluations, progress notes, copies of medication test results, and written informed consent forms. The PI is responsible for monitoring safety and data.

A subject may discontinue from this trial at any time, whether it is due to adverse effects or disinterest. All procedures have been designed to minimize subject discomfort and no subject will be asked to engage in research procedures not outlined in the consent form.

Describe the plan to be followed by the Principal Investigator/study staff for review of adverse events experienced by subjects under his/her care, and when applicable, for review of sponsor safety reports and DSMB reports. Describe the plan for reporting adverse events to the sponsor and the Partners' IRB and, when applicable, for submitting sponsor safety reports and DSMB reports to the Partners' IRBs. When the investigator is also the sponsor of the IND/IDE, include

the plan for reporting of adverse events to the FDA and, when applicable, to investigators at other sites.

NOTE: In addition to the adverse event reporting requirements of the sponsor, the principal investigator must follow the Partners Human Research Committee guidelines for Adverse Event Reporting

The Principal Investigator and the project medical staff will be available 24 hours per day via pager to respond to all reports of adverse events, including those that emerge outside of regularly scheduled visits.

Unanticipated problems involving risks to subjects or others including adverse events will be reported to the PHRC in accordance with PHRC unanticipated problems including adverse events reporting guidelines.

MONITORING AND QUALITY ASSURANCE

Describe the plan to be followed by the principal investigator/study staff to monitor and assure the validity and integrity of the data and adherence to the IRB-approved protocol. Specify who will be responsible for monitoring, and the planned frequency of monitoring. For example, specify who will review the accuracy and completeness of case report form entries, source documents, and informed consent.

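### The SAP's one analysis set needs about 2 weeks of exposure and is not limited to efficacy, so as written it drops children who stop early, including for harm, from the adverse-event analyses

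*SAP*

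**What the plan says.** The Statistical Methods section of the SAP opens with its only population rule: "Participants were included in the analysis based on a modified intent to treat analysis plan with the criterion that participants had to be exposed" to study treatment for about 2 weeks. The rule is stated for the analysis as a whole. Later in the same paragraph comes the safety analysis: "Adverse events (AEs) were analyzed using a Poisson regression model for AE counts and Fisher's exact tests for AE prevalence". No other population is named for it, and the protocol defines no analysis set or safety set.

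The protocol (Research Design and Methods) sets out a 6-week, open-label, randomised trial with 30 children per arm, designed to "compare efficacy and tolerability of the natural treatments omega-3 fatty acids, inositol, and NAC". On safety data it says: "Each week, a study clinician will record any adverse events".

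The ways out of the trial are in two places:

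- Research Design and Methods, drop criteria: "drop from the study will occur at clinician discretion for worsening of clinical course, non-compliance with treatment, or inability to tolerate study treatment". Also: "If a subject should score a 4 or higher on the C-SSRS, he or she will be dropped from the study".
- Data and Safety Monitoring: "A subject may discontinue from this trial at any time, whether it is due to adverse effects or disinterest".

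None of these three carries a minimum time on treatment. By contrast, the fixed poor-response rule needs a "CGI-bipolar score that is 2 points higher (more severe) than baseline for more than 2 consecutive weeks" (or a sustained rise in the P-YMRS over the same span), and the fixed compliance rule needs 2 weeks or longer.

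**The concern.** Exposure for 2 weeks is something that happens after randomisation, and an adverse event can prevent it. A child who stops in week 1 because of an AE would be left out of the AE comparison by the AE itself. AEs are recorded weekly, so data on such a child can exist and would be discarded. The window is a third of the treatment period.

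The exits that can operate inside that window include every harm-related one, while the two fixed rules for poor response and compliance can hardly act before it closes. The exclusion is therefore unlikely to be neutral for safety. Not every early exit is for harm, though: disinterest, missed visits and clinician discretion can also end participation early.

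What is at stake is the by-arm safety comparison. The two arms have different listed side effects (protocol, Foreseeable Risks and Discomforts), so unequal early withdrawal is possible. The protection of individual children during the trial is handled by the drop criteria and is not in question.

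**Working it through.** **No plan figure to reproduce.** The documents give no AE rate, early-exit rate or sample-size calculation. The only numerical inputs are 30 per arm and 6 weeks (protocol, Research Design and Methods), and two-sided alpha 0.05 and Fisher's exact test (SAP). All AE counts below are assumptions.

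**Step 1: direction within one arm.** Let an arm have n children, a of them with an AE. Suppose the 2-week rule removes k children with an AE and m without. Prevalence moves from a/n to (a−k)/(n−k−m).

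- Only AE leavers (m=0): (a−k)/(n−k) is below a/n whenever a is less than n. For 15/30 and k=3: 12/27 = 44.4%, against 50.0%.
- Only AE-free leavers (k=0): a/(n−m) is above a/n.
- Both: prevalence falls only if the share with an AE among those removed, k/(k+m), exceeds a/n. With k=1 and m=3 that share is 25%, below 50%, so 15/30 becomes 14/26 = 53.8% and prevalence rises.

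**Step 2: direction between arms.** Start from an assumed 15/30 (50.0%) v 6/30 (20.0%) and remove k AE leavers from one arm.

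| Arm losing children | k | Counts | Difference, points | Fisher p |
|---|---|---|---|---|
| none | 0 | 15/30 v 6/30 | 30.0 | 0.029 |
| higher-AE | 1 | 14/29 v 6/30 | 28.3 | 0.029 |
| higher-AE | 2 | 13/28 v 6/30 | 26.4 | 0.0497 |
| higher-AE | 3 | 12/27 v 6/30 | 24.4 | 0.086 |
| higher-AE | 5 | 10/25 v 6/30 | 20.0 | 0.140 |
| lower-AE | 3 | 15/30 v 3/27 | 38.9 | 0.002 |

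With 3 AE leavers removed from each of two arms at 15/30, the difference stays 0, but both arms read 44.4% and not 50.0%.

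**Step 3: a smaller contrast.** From 10/30 v 6/30 (p=0.38), removing 3 AE leavers from the first arm gives 7/27 v 6/30 (p=0.75). The difference falls from 13.3 to 5.9 points, with no change in the test conclusion.

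**Step 4: follow-up once early leavers are included.** Take 30 children with one AE each, 3 of whom leave at week 1. Child-weeks are 27×6 + 3×1 = 165, so the rate is 30/165 = 0.182 per child-week. Treating all as followed for 6 weeks gives 30/180 = 0.167, which is 8.3% too low (1 − 165/180). This is a consequence of the repair and not a fault shown in the SAP's own set; it is why the count model needs an offset.

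**The case against.** The strongest reply is that this is an ambiguity and not a demonstrated error. The SAP is a short text in the past tense with one general sentence on inclusion. The authors may have meant the rule for efficacy, or may have used all treated children for AEs. That stands as a limit: a reader might infer that the AE results were in fact computed in the 2-week set, and the documents do not show that. They show only that the one stated rule exempts nothing. The SAP also does not say in so many words that the AE tests compare arms; I infer it from the two-arm design, the tolerability aim and the use of Fisher's test.

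A reader might also infer that the rule always understates AEs, or always makes the arms look more alike. Steps 1 and 2 rule out both: AE-free leavers push prevalence up, and losses from the lower-AE arm widen the difference.

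Third, the number affected may be small or zero. The protocol reports minimal AEs in the group's earlier data (Background and Significance) and expects few side effects. The 50% v 20% example begins significant, so it has significance to lose; with k=2 it is still just below 0.05, and the smaller contrast in step 3 changes no conclusion. That is fair, and the figures are illustrations only.

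Finally, one might say that early harm withdrawals are hidden from a planned table. The SAP plans AE counts and prevalence, not withdrawals, so nothing planned is hidden; a by-arm count of withdrawals for harm is an addition.

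**Conclusion.** The point holds as a defect in how the safety population is specified. Followed as written, the SAP makes the AE comparison conditional on staying about 2 weeks, when a child can leave before then because of harm and with AE data already recorded. For a trial with tolerability as a comparative aim, that is more than missing detail.

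The size and direction of the bias are unknown. In the assumed examples, 3 early AE leavers move a 30.0-point difference to 24.4 or to 38.9 points, depending on the arm they came from. The conclusion rests on three assumptions: the lost sign means at least 2 weeks, the rule was applied to AEs as the text reads, and at least one child stopped before 2 weeks. If either of the last two fails, the reported AE results are unaffected and one clarifying sentence settles the matter. It is worth correcting because the cost is low.

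**What to change.** 1. State that the 2-week criterion applies to efficacy only.
2. Analyse AE counts and AE prevalence by arm in every randomised child who took at least one dose. Put log weeks on treatment in the Poisson count model as an offset, because follow-up then differs between children.
3. Report, by arm in the same set, the number of withdrawals for harm: AE, intolerance, or C-SSRS of 4 or higher. A C-SSRS drop may not have been coded as an AE, so it needs its own count.
4. If the analysis is complete, first confirm which set the AE models used. If it was all treated children, say so. If it was the 2-week set, rerun the AE analyses, label them as added after the SAP, and show both sets side by side.

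I would not add a comparison of each child's worst post-baseline C-SSRS score with baseline. It does not follow from the choice of analysis set, and taking the worst of six ratings against one inflates apparent worsening by chance.

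The cost is one or two sentences, a possible rerun of two existing AE analyses, and one small table. AEs and the C-SSRS are already collected weekly, so no new data are needed. The downsides are that the rerun may be post hoc, that intervals are wide at 30 per arm (0/30 has an exact two-sided 95% upper limit of 11.6%), and that small cells need care over identifiability. No efficacy result changes.

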5. History of sensitivity to omega-3 fatty acids, inositol or NAC. A non-responder or history of intolerance to omega-3 fatty acid, inositol or NAC after 2 months of treatment at adequate doses as determined by the clinician.
6. Severe allergies or multiple adverse drug reactions.
7. Unstable or untreated seizure disorder.
8. DSM-IV substance use, abuse or dependence.
9. Judged clinically to be at serious suicidal risk for C-SSRS score ≥ 4 .
10. Current diagnosis of schizophrenia.
11. Current diagnosis or symptoms of psychosis.
12. IQ < 70.
13. Pregnant or nursing.
14. Weighs less than 12.5kg.

The main outcome measures will be improvement in manic symptoms as measured by the Parent-Young Mania Rating Scale (P-YMRS) and improvement in depressive symptoms as measured by the parent-completed Children's Depression Inventory (CDI) scale.

Only subjects who are not responding to their current treatment regimen will be recommended to taper from their medications. No subject on a useful treatment will be recommended to taper from medication for entry into this study. Subjects and their current treating prescriber may opt to continue with current treatment even if taper is recommended. Typically, a 7-day washout period is recommended for antidepressant medications and atomoxetine (with the exception of Prozac requiring 14 days). Mood stabilizers/atypical antipsychotics are generally washed out over the course of 7 days, while stimulants are discontinued in 3 days. Discontinuation of medications will be done in consultation with the prescribing clinician.

We plan to treat subjects with the following doses:

Omega-3 Fatty Acids

All subjects: 1020mg QAM + 1020mg QPM

+

Inositol

Subjects under 25kg: 1000mg daily

Subjects weighing 25kg or more: 2000mg daily

OR

NAC:

Effervescent Tablets

Subjects ages 5-12: 1800mg daily

Subjects ages 13-17: 2700 mg daily

Capsules

Subjects ages 5-12: 1800mg daily

Subjects ages 13-17: 2400mg daily

At each visit, measures of safety and effectiveness will be obtained using rating scales.

Briefly describe study procedures. Include any local site restrictions, for example, "Subjects enrolled at Partners will not participate in the pharmacokinetic portion of the study." Describe study endpoints.

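### The primary group-by-week test uses mixed-effects Poisson models of rating-scale scores with no stated random slope or robust variance; with default errors its p-value can be too small or too large.

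*SAP*

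**What the plan says.** The SAP's Statistical Methods section is the only statistical text in the two documents.

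- **Outcomes.** It covers "Primary efficacy measures of mania and depression, as well as secondary measures of autism symptoms and executive functioning". The protocol (Research Design and Methods) defines the main outcomes as "improvement in manic symptoms as measured by the Parent-Young Mania Rating Scale (P-YMRS) and improvement in depressive symptoms" on the parent-completed CDI. P-YMRS and CDI are completed at baseline and at the weekly visits; SRS and BRIEF at baseline and endpoint only.
- **Model.** These scores "were analyzed using mixed-effects Poisson regression models predict the outcome measure of interest from the study group, study week (continuous") and their interaction.
- **Primary term.** The SAP names "the study group-by-study week interaction, which is the primary effect of interest".
- **Test.** "All analyses were two-tailed with an alpha level of 0.05 and conducted using Stata (Version 18.1").
- **Analysis set.** A modified intent-to-treat set in which "participants had to be exposed to the study medications for" a two-week threshold. The number analysed is not given.
- **Moderators.** "we added a 3-way interaction term between study group, study visit, and CBCL profile group to each of the models"; this covers both outcome tiers.

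The term mixed-effects implies at least one random effect. The SAP does not say whether that is an intercept only or also a slope on week, how the variance was estimated, or whether dispersion was checked. Its score limits (SRS 30-90, BRIEF 30-100, YMRS up to 60, CDI up to 40) belong to the truncated Poisson comparisons at baseline, not to the efficacy models.

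**The concern.** A Poisson likelihood sets the variance of a score, given the child's random effects, equal to its mean. These outcomes are bounded rating-scale scores, and nothing in the documents supports that equality.

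Two assumptions feed directly into the standard error of the primary term:

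1. **Dispersion.** If within-child variance is below the mean, default errors are too wide and the test is conservative. If it is above the mean, they are too narrow.
2. **Rate of change.** A random intercept absorbs differences in level between children but not in rate of change. If children change at different log rates and no random slope is fitted, default errors are too narrow.

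A random slope deals with the second but leaves conservatism from the first. Participant-level robust errors largely deal with both. At stake is whether the trial's main comparison keeps its 5% error rate; a reader cannot tell from the plan.

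**Working it through.** The plan gives no power, SD or dispersion figure, so there is nothing of its own to reproduce except the nominal 5%.

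**Inputs from the documents:** two-sided 0.05; 60 children planned, 30 per arm; six weeks, taken as visits 0-6 for P-YMRS and CDI; two visits for SRS and BRIEF; the two-week exposure criterion.

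**Assumed inputs:** all means, SDs and dropout. Unless stated: 50 children analysed, no treatment difference, 20% leaving at random after week 2. P-YMRS falls 15 to 10, 22 to 15 or 30 to 20; CDI falls 12 to 9, 18 to 14 or 24 to 19. Residual SD is 4 (P-YMRS) or 3.5 (CDI).

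**Step 1: dispersion alone.** If within-child variance is φ times the mean, the real error rate is about 2 × [1 − Φ(1.96/√φ)].
- φ = 0.5: 1.96/0.707 = 2.77, giving 0.6%.
- φ = 1: 5.0%.
- φ = 1.5: 1.96/1.225 = 1.60, giving 10.9%.
- φ = 2: 1.96/1.414 = 1.39, giving 16.6%.

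Simulation with 30 per arm gave 0.4%, 4.8%, 10.9% and 16.5%.

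**Step 2: dispersion and differing change, random intercept, default errors.** Simulated type I error (%), 1,400 runs per cell, by SD of true six-week change in points:

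| Scale, baseline mean | SD 0, smaller residual SD* | SD 0 | SD 3 | SD 5 | SD 7 |
|---|---|---|---|---|---|
| P-YMRS 15 | 4.1 | 10.2 | 17.6 | 27.0 | 32.9 |
| P-YMRS 22 | 2.6 | 5.6 | 12.3 | 18.2 | 30.1 |
| P-YMRS 30 | 2.6 | 4.8 | 9.5 | 17.4 | 24.6 |
| CDI 12 | 2.6 | 7.6 | 16.4 | 24.1 | – |
| CDI 18 | 0.2 | 4.3 | 9.1 | 18.9 | – |
| CDI 24 | 0.4 | 1.8 | 6.5 | 13.5 | – |

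*Residual SD 3 for P-YMRS, 2.5 for CDI.

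A rerun by conditional Poisson regression gave 0.1-35.5% across its cases. A further simulation with 30 per arm, Poisson scores and log-slope SD 0.10 per week (0.6 over six weeks, a wide spread) gave 49.3%, so the top of the range depends on the assumed spread.

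**Step 3: reading the SD 0 columns.** There every child falls by the same number of points. On the model's log scale that is still variation in slope. With a common proportional fall, conservatism is stronger: P-YMRS mean 22, residual SD 3, gave 2.7% additive and 0.5% proportional. The Step 1 formula agrees: φ ≈ 9/18.5 = 0.49, giving 0.5%.

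**Step 4: the other readings.** Random slope with default errors: 4.2-6.3% at SD 3-7, but 0.1-6.1% at SD 0. Participant-level robust errors, t on children minus 2: 3.9-5.9% (random intercept) and 2.7-5.4% (random slope); the conditional Poisson rerun gave 4.0-6.3%. With a normal cut-off, robust errors gave 4.9-6.3% at 30 per arm and 7.1% at 20 per arm.

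**Step 5: analysed number.** P-YMRS mean 22, SD 5, with 40 / 50 / 60 children: 19.9 / 18.2 / 21.6% default; 5.9 / 3.9 / 5.1% robust.

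**Step 6: two-visit scales, random intercept.** Default errors are about right when the SD of observed change equals √(baseline mean + endpoint mean):
- √(55 + 52) = 10.3
- √(65 + 62) = 11.3
- √(75 + 71) = 12.1
- √(80 + 76) = 12.5

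The error rate is about 2 × P(Z > 1.96 × break-even/SD): 0.0-0.4% at SD 7 and 8.0-14.8% at SD 14 (9.1% at mean 75). Simulation at mean 75 with scores held to 30-90 gave 0.0-0.2% at SD 7 and 5.9-7.1% at SD 14. Those limits are the SRS limits, so the simulated figures do not describe BRIEF. At SD 14, a check gave 6.1% with a cap of 90 and 10.2% with a cap of 100.

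**The case against.** The strongest reply is that no error has been shown. The SAP is a short summary in the past tense, and an unstated option may still have been used. Robust errors would make the point moot, and a random slope would leave at most conservatism, so serious inflation needs one particular reading. That stands.

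It also stands that no document figure fixes the size. The 32.9% cell is a corner case: the true endpoint has mean 10 and SD √(25 + 49) = 8.6 (between-child SD 5, change SD 7), so about 12% of true values fall below zero and are cut at the floor.

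A reader might infer that the primary p-value is too small, or that Poisson models are invalid for these scales. The documents support neither: direction depends on dispersion and slope spread, which they do not give, and the same model with robust errors keeps close to 5% in these cases.

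The objection does not remove the point. The model as named ties variance to the mean, nothing in the plan relaxes that, and this is the primary test.

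**Conclusion.** The concern holds in conditional form. What is established is that the SAP does not state the random-effects structure or variance estimator for its primary test, and that the named model with default errors is calibrated only under conditions the documents do not support. Whether the actual p-value is affected, by how much and in which direction is unknown.

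The illustrative size is about 0-35% type I error with a random intercept and default errors, against about 4-6% with participant-level robust errors, and up to about 7% in small samples. These figures rest on assumed means, SDs and random dropout. It should be fixed because it concerns the primary effect and the remedy is cheap; confidence is medium.

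**What to change.** 1. State the random effects and variance estimator actually used, and report observed dispersion and SD of change for each scale. If participant-level robust errors were already used, saying so is enough.
2. Otherwise, report group-by-week confidence intervals and p-values from the same models with participant-level sandwich standard errors and a t reference. Label them post hoc and show them beside the original result.
3. Set the degrees of freedom from the children who contribute to the term, minus 2. For P-YMRS and CDI these are the children in the modified-ITT set (38, 48 or 58 for 40, 50 or 60 children; critical values 2.024, 2.011 and 2.002). For SRS and BRIEF they are the children with both baseline and endpoint forms.
4. If the two results disagree at 5%, say that the conclusion depends on the variance assumption.
5. Treat the moderator models as exploratory; robust errors are less stable in those subgroups.

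**Cost.** A few sentences and one variance option per existing model, with no new data and no change of estimand. In the simulated cases with SD of change 3-7, robust intervals were 1.05 to 2.12 times the default width with a random intercept only and 0.98 to 1.07 times with a random slope; in the SD 0 cases, 0.66 to 1.21 times. Robust errors can be slightly liberal at this size: two sets of two-visit runs gave 3.8-5.4% and 6.1-7.0%. They do not correct bias from outcome-related dropout.
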